3.3.5. Number of Clinician-Recommended CMV Monitoring Tests Completed

The clinician-recommended CMV monitoring tests actually completed are entered into the data system on the CMV Test Results (CTR) – Chart Review eCRF. The number of tests completed will be the number of records entered on this eCRF that were collected on or prior to the end of follow up date or, as a sensitivity analysis, the maximal possible study period end date.

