3.1.2 Primary Objective

To evaluate adherence to recommended CMV monitoring duration and interval during the first year after HCT upon enrollment using subject collected dried blood spot testing

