3.1.4 Exploratory Objectives

- 1. Evaluate the transit time from self-collection to arrival in the laboratory
- 2. Assess the mechanism for non-compliance as defined by a missing DBS sample PCR result (e.g. mobile technology failure, sample collection failure, sample delivery failure, sample viability failure)
- 3. Compare the performance characteristics of concurrently drawn DBS with plasma CMV PCR (e.g., sensitivity and specificity concordance)
- 4. Determine if the randomized study population is representative of the population as a whole
- 5. Obtain a population-based estimate of late CMV disease in observational and randomized cohorts
- 6. Describe local provider CMV treatment algorithms
- 7. Assess subject and provider satisfaction of DBS testing

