not possible these supervised trainings may be completed remotely via video conferencing as an option (See MOP for details and instructions). The third session will be unsupervised with the subject performing the testing in their home or temporary residence nearby the transplant center This training session will be followed up with a phone call or in-person check-in and a questionnaire to assess understanding. At each session, the subject will have written instructions on performing the DBS testing and utilizing the web/mobile technology available for their reference. Each DBS training session requires the completion of a DBS collection. The study coordinator will be available to provide additional training session as needed. In addition, DBS collection instructional video is available on the study website. Prior to discharge from the transplant care team, study personnel must confirm that the subject demonstrates proficiency in DBS sample collection and use of the study website.

The mobile technology will consist of a notification system that sends weekly reminders by email and/or text message determined by the subject's preference to the subject to complete DBS self-collection procedures. The notifications are sent from a web-based, 21 CFR 11-compliant electronic data capture system created and maintained by The Emmes Company. The subject will log into the system on a computer or mobile device with internet access to set up study reminders and record sample collection and shipment information. The system will also house IRB-approved training materials and the web address of the United States Postal Services (USPS) so that shipments may be scheduled.

Subjects who are enrolled in the control arm of the randomized study will continue to receive their office-based CMV plasma testing as recommended by standard of care.

Quarterly follow-up contacts will be made with the primary care physicians of all randomized subjects enrolled in the study to obtain each subject's medical record. Data from each subject's medical record on immunosuppression, CMV disease status, any interim use of antiviral therapy for CMV disease or plasma reactivation, clinically recommended CMV test interval, any hospitalization record, relapse, and survival status will be collected.

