7.5 Follow-up (Quarterly, ± 2 weeks)

Quarterly follow-up contacts will be done on all randomized subjects while enrolled in the study regardless of the randomization status. Study sites will follow up with subjects' primary care physicians to obtain the following records at each quarterly time point based on transplant date:

- Current immunosuppression
- Systemic steroid use
- Recommended CMV test interval (i.e., testing frequency)
- Office-based CMV test dates and results (i.e. PCR, IHC, histopathology, etc.)
- Interim hospitalizations
- CMV disease status
- Interim use of preemptive therapy for late CMV disease
- AEs
- Date of morphological relapse
- Survival status
- Problems with DBS or plasma kit integrity

If the scheduled quarterly visit is within 10 days of subject randomization, the corresponding quarterly visit will be waived.

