11 STATISTICAL CONSIDERATIONS

11.1 Study Outcome Measures

11.1.1 Primary Endpoint

The primary endpoint will be the proportion of subjects who complete >90% of their recommended CMV monitoring tests by 1-year post-transplant. We will use logistic regression modeling to compare this proportion between subjects randomized to DBS testing versus standard office-based testing. Since randomization will be stratified by transplant site and subject's perceived ease of access to blood draw facility, these factors will be used as adjustment factors in the models.

For each subject, the number of CMV monitoring tests performed will be assessed and the percent of recommended tests will be calculated. Subjects with percent completion >90% will be considered a success with regard to the primary endpoint. The personspecific denominator for the proportion, number of expected CMV monitoring tests, will be variable and dependent on subjects' immunosuppression and hospitalizations during the study. For example, subjects in this study that are highly immunosuppressed a weekly monitoring schedule is generally recommended, often throughout the first year after transplantation. If such a subject were discharged from the primary transplant center at day 100, there would be 38 remaining tests until day 365 after HCT (if the subject is still alive at 1 year). We will assess the actual number of tests performed and calculate the percent of tests (e.g. 36/38 = 94.7%). Another scenario would be for a subject that stopped monitoring and was then re-started on high-dose steroids for treatment of GVHD with resumption of weekly testing, resulting in yet another denominator. Study participants in the DBS arm who are hospitalized during the study should not collect DBS samples while admitted. Rather, admitting hospitals should monitor participants for CMV with plasma CMV DNA PCR testing as recommended for their level of immunosuppression. Those inpatient testing timepoints will not be included in the person-specific denominator.

The primary analysis will be an intent-to-treat (ITT) analysis of all subjects randomized. Another key analysis will be the modified intent to treat analysis of all subjects who had at least one test done after discharge from the primary transplant team.

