11.1.2 Secondary Endpoint

As a secondary endpoint we will be comparing the incidence of late CMV disease by one year post HCT between the two randomized groups using competing risk regression with death treated as a competing risk event ⁴². Using similar methods, we will also compare the CMV disease incidence of trial participants compared to subjects who received HCTs at the clinical sites in the similar time period but did not participate in the trial. As expected, the planned trial would not be sufficiently powered to detect a difference in late CMV disease incidence from 8% (current standard care) to 2% (observed in clinical trial). A trial powered for that detectable effect size would require 330 subjects to have 80% power (one-sided p values 0.05).

To determine the rate of CMV disease at participating sites during the clinical trial we will collect concurrent retrospective baseline data as well as CMV disease and survival data from subjects that were eligible for randomization but decided not to participate (the majority of subjects return to the transplant center at one year). The purpose of this analysis is to determine whether the subjects who participated in the trial are representative of the population at risk for late CMV disease and whether the phenomenon of late CMV disease continues to occur throughout the study period.

To assess the correlation of CMV viral load between DBS and plasma samples, we will use linear model. Other outcomes will be tabulated and compared between groups using Chi-Square, Fisher's exact, and log rank tests, as appropriate.

The relative contribution of mobile phone reminders, subject adherence to the device, and failures of the testing kit itself will be analyzed among subjects randomized to the DBS arm who did not reach the 90% adherence threshold.

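### The SAP counts only chart-review (office) tests as completed in both arms, an undeclared conflict with the DBS-based objective, comparison and power basis

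*SAP*

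**What the plan says.** **SAP, numerator.** Section 3.3.5 says of the Chart Review eCRF: "The number of tests completed will be the number of records entered on this eCRF". It gives no separate rule for the DBS arm. Section 4.5.1 divides this count by the expected count to obtain the primary endpoint, and 4.5.2 and 8.2 carry it into the secondary one. DBS results are stored elsewhere: the footnotes to Table 5 take office tests from the Chart Review form and DBS samples from the Laboratory Data Upload form, and Listing 9 labels the two as distinct sources.

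**Protocol, endpoint.** Section 11.1.1 says only that "the number of CMV monitoring tests performed will be assessed and the percent of recommended tests will be calculated". It does not say which tests count in the DBS arm.

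**Protocol, purpose.** The primary objective (3.1.2) is adherence "upon enrollment using subject collected dried blood spot testing"; SAP 3.1.1 repeats it with one word changed. Section 4.1 says "Subjects who are enrolled in the control arm of the randomized study will continue to receive their office-based CMV plasma testing". The primary model is to "compare this proportion between subjects randomized to DBS testing versus standard office-based testing" (11.1.1). Reminder, adherence and kit failures "will be analyzed among subjects randomized to the DBS arm who did not reach the 90% adherence threshold" (11.1.2). Protocol 11.2 and SAP 5 both rest the power statement on showing high completion with collected DBS monitoring.

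**SAP section 17** declares one change, the sensitivity analysis without the University of Minnesota.

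**The concern.** Followed as written, the primary p-value compares office testing with office testing. A DBS participant who returns every weekly card but has fewer office draws is a failure. The trial could then report a null or positive result without saying whether DBS monitoring achieves more than 90% of recommended tests, which is the question its objective and sample size were written for.

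Nothing else in the plan fills the gap. Tables 14 to 19 all use the clinician-recommended count, Tables 39 and 40 describe DBS compliance in the DBS arm alone, and SAP 8.3 plans no exploratory adherence analysis.

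**Working it through.** **1. Which reading does each passage support?**

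- *DBS results count:* the objective in both documents; the DBS-versus-office comparison (protocol 11.1.1); kit failure as an explanation for falling below 90% (11.1.2), since a faulty kit cannot directly explain a missed office draw; removal of inpatient timepoints from the denominator for hospitalised DBS participants, who may not collect cards then (11.1.1); and the power basis (protocol 11.2, SAP 5).
- *Only office tests count:* SAP 3.3.5; SAP 4.2, where DBS is collected alongside clinician-recommended monitoring; SAP 4.4.1, where both arms have care-team samples; SAP 6.3.1, which speaks of in-office tests.
- *Either:* protocol 7.5 collects "Office-based CMV test dates and results" for all randomized subjects, and 2.1.6 lets a reminder prompt a DBS collection or an office visit.

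**2. Reproduce the stated power.** Inputs (protocol 11.2, SAP Table 2): 100 DBS, 50 control, two-sided 0.05, DBS rate 0.80, control rate 0.50, 0.55 or 0.58. Pooled normal approximation:

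power = Φ[(|p₁ − p₀| − 1.96·SE₀)/SE₁], SE₀ = √[p̄(1−p̄)(1/100 + 1/50)], SE₁ = √[p₁(1−p₁)/100 + p₀(1−p₀)/50].

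For 0.80 v 0.50: p̄ = (80 + 25)/150 = 0.70; SE₀ = √0.0063 = 0.0794; SE₁ = √0.0066 = 0.0812; (0.30 − 0.1556)/0.0812 = 1.78; power 96.2%. For control 0.55 and 0.58 the formula gives 88.5% and 80.3%. The stated 96%, 89% and 80% are reproduced.

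**3. Power under the SAP's numerator.** The DBS-arm rate becomes the share with more than 90% of *office* tests done. The documents do not give this rate, so those below are assumptions.

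| DBS-arm office rate (assumed) | v control 0.50 | v control 0.55 |
|---|---|---|
| 0.40 | 21.4%, favouring control | 41.3%, favouring control |
| 0.60 | 21.4% | 8.6% |
| 0.70 | 66.7% | 44.4% |
| 0.80 | 96.2% | 88.5% |

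For 0.70 v 0.50: p̄ = 95/150 = 0.633; SE₀ = 0.0835; SE₁ = √0.0071 = 0.0843; (0.20 − 0.1636)/0.0843 = 0.43; power 66.7%.

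**4. One participant.** With discharge at day 100 and a weekly schedule, Appendix 4 gives floor((365 − 100 + 1)/7) = 38 expected tests, the protocol's own example. Success needs 35 (35/38 = 92.1%; 34/38 = 89.5%). Someone with 38 DBS results and 34 office tests fails.

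**5. Does a DBS-inclusive count have its own problem?** Yes, on sparse schedules. A monthly recommendation from day 100 gives floor(266/30) = 8 expected tests, and all 8 are needed (7/8 = 87.5%). Suppose each arm completes 80% of its own scheduled tests, independently. Office success is 0.8⁸ = 16.8%. Each 30-day interval holds at least four weekly DBS dates, so if any one card meets the monthly test, success is at least (1 − 0.2⁴)⁸ = 98.7%. On a weekly schedule each arm has one scheduled test per expected test.

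**The case against.** The strongest reply is that the office-only count is a deliberate, coherent add-on design. SAP 4.2 describes DBS as collected simultaneously with clinician-recommended monitoring, and 4.4.1 and 6.3.1 agree. Protocol 7.2.1 tells DBS participants to give plasma at clinical draws, and 7.2.2 makes the control arm's activities the same apart from DBS collection. The exploratory objective, "Assess the mechanism for non-compliance as defined by a missing DBS sample PCR result", and SAP 3.3.8 on missed DBS tests can belong to a separate family of DBS-compliance analyses, which SAP 3.3.2 names. DBS is weekly throughout, while the primary denominator follows the clinician's changing recommendation. Section 17 lists changes, and one may say the SAP only settled what the protocol left open.

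Most of this stands. A reader might infer that the SAP breaches a protocol definition; it does not, because the protocol has no such sentence. The passages on missing DBS results are weak evidence and the conclusion does not rest on them. What the reply leaves unanswered is the objective that the SAP itself repeats, the protocol's comparison and kit-failure analysis, and a power basis expressed in DBS monitoring. A deliberate choice that changes what the primary result means still needs declaring.

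It is also fair that counting any weekly card towards a sparse schedule favours the DBS arm (step 5). The fix has to allow for that.

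**Conclusion.** The conflict is real, lies between and within the documents, and should be resolved before database lock. As written, no self-collected DBS result reaches the primary or secondary adherence endpoint, and no planned analysis compares DBS-inclusive completion with control.

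Two stronger conclusions are tempting and unsupported. The first is that the power calculation is wrong. Its arithmetic reproduces; only the 80% input lacks a documented basis for office tests. The second is that the analysis is biased against DBS. The direction is unknown: DBS may replace office draws, or reminders and positive results may prompt more of them. The 21% and 67% figures illustrate how much depends on an unstated rate; they do not estimate the trial's power.

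The conclusion assumes that DBS results are not also abstracted onto the Chart Review form. The documents do not rule this out, but Table 5 and Listing 9 treat the sources as separate.

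**What to change.** Before database lock:

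1. State in SAP 3.3.5 and 4.5.1 which records count as completed in each arm. Align the objective and power wording with that choice and record it in section 17.
2. Pre-specify a between-arm ITT analysis in which a recommended test is met in the DBS arm by an evaluable scheduled DBS result or a chart-review CMV PCR, and in the control arm by a chart-review CMV PCR. Credit at most one test per expected test, cap the proportion at 1, and take inpatient timepoints out of the denominator as protocol 11.1.1 provides; Appendix 4 does not do so now. Report it also limited to periods with a weekly recommendation, because of step 5. The University of Minnesota has no recorded schedule; handle it with the exclusion sensitivity analysis already planned. No elaborate interval algorithm is needed.
3. Report the office-only count beside it. If that count stays primary, restate the objective accordingly and say that the 80% DBS-arm rate and the stated power were not derived for that endpoint.

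The cost is an SAP amendment and derivation code. Protocol 11.5 already allows the analysis plan to be amended before lock. DBS results, dated office tests and, outside Minnesota, recommended intervals are already recorded, so no new data are needed.

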3.3.2. Study Period

The study period for all safety analyses is defined as the time from enrollment to End of Follow-up.

The study period for all adherence analyses and DBS collection compliance analyses is the time from discharge to End of Follow-up. For participants in the DBS arm who were hospitalized during the follow-up, the duration of hospitalization will be subtracted from the study period for assessment of compliance with DBS collection.

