4.5. Adherence and Safety Variables

4.5.1. Primary Outcome Measures

• The primary outcome is the number of participants in each intervention group who complete >90% of their clinician-recommended CMV monitoring tests in the study period (Section 3.3.2), by 1-year post-transplant.

The proportion of clinician-recommended CMV monitoring tests completed will be defined for each participant as the number of clinician-recommended CMV monitoring tests completed divided by the number of recommended clinician-recommended CMV monitoring tests, where the number of clinician-recommended CMV monitoring tests are defined as in Section 3.3.

The primary outcome measure will be considered a binary variable based on each participant's observed proportion of clinician recommended CMV monitoring tests completed:

- Met > 90% threshold: the participant completed > 90% of their clinician recommended CMV monitoring tests (Success)
- Did not meet > 90% threshold: the participant completed < 90% of their clinician recommended CMV monitoring tests (Fail)

Participants who withdraw prior to discharge will be considered as fail, i.e. not meeting the >90% threshold. Participants who didn't have recommended monitoring test scheduled will also be considered as fail.

The primary and secondary adherence outcomes will be analyzed with ITT, mITT and completer populations during the Study Period defined in Section 3.3.2. A sensitivity analysis will be conducted to exclude all participants from the University of Minnesota for the primary and secondary adherence measures.

In addition, sensitivity analyses with Maximal Study Period defined in Section 3.3.3 will be performed with ITT, mITT and completer populations with and without the participants from the University of Minnesota.

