8.2. Secondary Adherence Analyses

A fractional logistic regression model will be fit with quasi-maximum likelihood estimates in the ITT population where the outcome will be the proportion of recommended monitoring tests completed per participant, and the covariates will be randomized intervention group and the stratification variables. This fractional response model was introduced by Papke and Wooldridge (1996) in their frequently cited extension of the generalized linear model to analyze proportion data that are bounded by 0 and 1. Although commonly applied to these outcome data for simplicity, ordinary least squares regression assumes that the predictor variables and continuous outcome variable are linearly related and that the variance is independent of the mean, the violations of which in models of fractional outcomes result in biased estimates and potentially misleading inference. The marginal effects of predictor variables on the mean proportion response can be estimated using the binominal likelihood framework with robust standard errors. Appropriate to the proportion outcome data, the model allows for responses at the 0 and 1 boundaries, in contrast to the beta regression approach that has been described for proportion data that do not include extremes (zero or one).

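### The primary-endpoint numerator is an unmatched, uncapped count of chart records, so extra post-discharge tests can offset missed ones and completion can exceed 100%

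*SAP*

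**What the plan says.** **Numerator.** SAP 3.3.5 introduces the Chart Review eCRF by saying that "The clinician-recommended CMV monitoring tests actually completed are entered into the data system" there. The counting rule follows: "The number of tests completed will be the number of records entered on this eCRF". The same sentence limits this to entries "that were collected on or prior to the end of follow up date", with the end of the maximal possible study period as the limit in the sensitivity analysis. The only date limit in that section is an upper one.

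**Ratio.** SAP 4.5.1 uses "the number of clinician-recommended CMV monitoring tests completed divided by the number of recommended clinician-recommended CMV monitoring tests". A value above 90% is a success. Protocol 11.1.1 works the same way, with a worked example in per cent: "We will assess the actual number of tests performed and calculate the percent of tests (e.g. 36/38 = 94.7".

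**Window.** SAP 3.3.2 states: "The study period for all adherence analyses and DBS collection compliance analyses is the time from discharge to End of Follow-up". SAP 4.5.1 refers to it, counting those who "complete >90% of their clinician-recommended CMV monitoring tests in the study period (Section 3.3.2), by 1-year post-transplant".

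**Denominator.** SAP 3.3.4 and Appendix 4 add up due tests from discharge, one monitoring schedule at a time. Item 4 of the Appendix 4 notation ends the sum at the end of the study period or, if earlier, when monitoring stops being required.

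**What sites abstract.** Protocol 7.5 and 7.6 ask for office-based CMV tests and name PCR, immunohistochemistry and histopathology.

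**Hospital stays.** Protocol 11.1.1 takes inpatient time points out of the denominator, in text written for the DBS arm. SAP 3.3.2 subtracts hospital days only when assessing DBS collection, and Appendix 4 has no hospital term. No section says what happens to inpatient records in the numerator.

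**Secondary model.** SAP 8.2 chooses fractional logistic regression as a way to "analyze proportion data that are bounded by 0 and 1".

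**The concern.** The two halves of the ratio measure different things. The denominator is a set of due dates; the numerator is a number of events. They agree only if each record answers one due test, and no rule makes that so. Repeat tests in one week, tests after monitoring was stopped, and chart results that were not surveillance tests can each fill the place of a missed week.

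The endpoint is meant to show whether people at risk of late CMV disease are tested on schedule. Someone with long untested gaps and a cluster of tests around one CMV episode could count as adherent. This is the trial's only primary outcome, and its threshold leaves little slack, so a few records decide success or failure. If extra testing differs between arms, the error becomes bias and not just noise.

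**Working it through.** **1. The plan's own figures reproduce.**
- Protocol 11.1.1: 36/38 = 94.7%.
- Appendix 4 Example 1: floor(305/7) = 43 due tests. Example 2, first interval: floor(185/7) = 26.
- Power (SAP Table 2): n = 50 and 100, success p1 (control) and 0.80 (DBS), two-sided 5%. Power = Φ[(d − 1.96·se0)/se1], where d is the difference, se0 uses the pooled proportion and se1 the separate ones. For p1 = 0.55: pooled = (27.5 + 80)/150 = 0.717, se0 = 0.0780, se1 = 0.0809, so Φ(1.20) = 88.5%, against 89% stated. For 0.50 and 0.58 it gives 96.2% and 80.3%, against 96% and 80%.

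**2. How many misses the threshold allows.** The smallest passing count is floor(0.9·D) + 1 for D due tests.

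| Due tests D | Needed to pass | Misses allowed |
|---|---|---|
| 26 | 24 | 2 |
| 38 | 35 | 3 |
| 43 | 39 | 4 |

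**3. Extra records in weeks already tested.** Compare covered/D (each due test credited once) with (covered + extra)/D (SAP 3.3.5).

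| D | Covered | Credited once | Extra records | Raw count |
|---|---|---|---|---|
| 38 | 30 | 78.9%, fail | 5 | 35/38 = 92.1%, success |
| 43 | 35 | 81.4%, fail | 4 | 39/43 = 90.7%, success |
| 38 | 30 | 78.9%, fail | 9 | 39/38 = 102.6%, success |
| 38 | 38 | 100%, success | 2 | 40/38 = 105.3%, success |

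The last two rows lie outside the range that SAP 8.2 assumes, and the plan does not say how to handle them.

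**4. Records after monitoring has ended.** Suppose monitoring stops at the end of the first interval of Example 2, with 26 tests due and 22 covered: 22/26 = 84.6%, fail. The denominator is closed, but SAP 3.3.5 goes on counting to the end of follow-up. Two later records give 24/26 = 92.3%, success.

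**5. Size under assumed inputs.** The documents give neither the spread of adherence nor a rate of extra tests. Take 38 weekly due tests, a personal weekly adherence drawn from a beta distribution, and extra post-discharge records that are Poisson. Success needs at least 35.

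| Adherence distribution | Credited once | Raw, mean 1 extra | Raw, mean 2 extra |
|---|---|---|---|
| Beta(6, 1), many people near 90% | 46% | 53% | 60% |
| Beta(0.4, 0.2), U-shaped | 46% | 48% | 50% |

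Under Beta(6, 1) with a mean of two extras, 24% of participants exceed 100%.

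**6. If extras helped only one arm.** Hold DBS at 80% and let extra records lift control success from 55% to 60%. Then se0 = 0.0766, se1 = 0.08, and power = Φ[(0.20 − 1.96 × 0.0766)/0.08] = Φ(0.62) = 73%, down from 88.5%. This shows sensitivity; nothing in the documents says that this would happen or in which arm.

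**The case against.** The best defence is that the SAP follows the protocol, which divides tests performed by tests expected, and that SAP 3.3.5 describes the form as holding recommended tests. If sites enter only those, extras would be few. That description is not a rule, though: nothing says which chart results qualify, the protocol's abstraction list goes beyond surveillance PCR, and every record is then counted. The point about entry practice does stand against any claim that inpatient or diagnostic tests are certainly in the numerator. The abstraction item concerns office-based tests, so their inclusion is possible but not established.

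Three stronger readings are tempting and do not hold.
- A reader might infer that the numerator has no start date, so that tests before discharge count. SAP 3.3.2, 3.3.3 and 4.5.1 place the adherence window from discharge onward. SAP 3.3.5 only fails to repeat that limit, which is a gap in wording.
- A reader might infer that a positive DBS inflates the DBS arm through its confirmatory blood draw. SAP 3.3.9 and 3.3.10 put those results on the Laboratory Data Upload eCRF, not on the Chart Review eCRF that is counted. Further local testing could follow a positive result, but no rate is given.
- A reader might take the 60% in step 5 as a forecast. The U-shaped distribution, with the same 46% starting point, gives 50%.

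Two practical objections also stand. A rigid window of one interval would fail someone who tests every week but drifts by a day or two, leaving two tests in one window and none in the next. And matching needs a schedule, which SAP 3.3.4 says the University of Minnesota did not record.

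**Conclusion.** As written, SAP 3.3.5 and 4.5.1 allow extra post-discharge records to offset missed due tests, and allow a proportion above 1 that contradicts the range assumed in SAP 8.2. Both follow from the definitions alone. At the protocol's example of 38 due tests, five extra records turn 78.9% coverage into a success.

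How much this moves the trial result is not known. Under the assumptions in step 5, a mean of two extra records adds about 4 to 14 percentage points to the success rate. Net bias between arms could run in either direction or be absent. The rule should be settled before analysis, because choosing it afterwards could change who counts as a success.

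**What to change.** Amend SAP 3.3.5 as follows.
1. Count only CMV PCR records dated after discharge and inside the Appendix 4 monitoring intervals. Say which date is used: 3.3.5 speaks of collection, while the Listing 9 footnote gives test dates for chart-review results.
2. Credit each due test at most once, using a pre-specified window that tolerates small shifts in test day. The proportion then cannot exceed 1.
3. Treat hospitalised periods the same way in numerator and denominator and in both arms, and reconcile protocol 11.1.1 with SAP 3.3.2 and Appendix 4 on this.
4. Keep the raw count, capped at 1, as a sensitivity analysis.
5. State that matching cannot be applied at the site with no recorded schedule, and report the matched analysis with that site excluded. SAP 3.3.4 keeps that site in the primary ITT analysis, so the text must say how the two fit together.

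The cost is SAP wording and some programming; test dates are already abstracted. Success rates will be somewhat lower than under the raw count.
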